The sponsor will collect Changes in Tinnitus and/or Pain visual analog scale scores from any subject reporting tinnitus or chronic pain during each point of administration, including baseline, experimental and integrative sessions, the primary endpoint, and two-month follow-up. The sponsor will plot out and examine all changes in tinnitus and/or pain visual analog scale scores across both groups and in each active dose group and the comparator dose group for trends. Formal analysis of changes in tinnitus and/or pain visual analog scale scores will only occur if three or more subjects complete changes in tinnitus and/or pain visual analog scale at baseline and primary endpoint. Likewise, formal between-groups analyses will not be performed if all primary endpoint scores are from subjects assigned to the same condition. The sponsor will perform an independent t-test on the difference between baseline and primary endpoint Changes in Tinnitus and/or Pain visual analog scale scores between each active dose and comparator dose conditions, with p. set at 0.05. If the only scores available are for subjects in a single condition, then a paired t-test will be performed comparing baseline and primary endpoint Changes in Tinnitus and/or Pain visual analog scale scores, with p. set at 0.05.

Perception of the experimental sessions will be examined during Stage 1 and Stage 2, before and after subjects have undergone a third experimental session. The results of this exploratory analysis will inform the sponsor of expectancies and the value of the third session for future protocol development. These data may be correlated with primary/secondary endpoint CAPS data compared to end of Stage 1/Stage 2 CAPS data to assess the potential contribution of expectation and self-reported response to changes in PTSD symptoms.

The sponsor will compare CAPS, PDS, PTGI, GAF, BDI-II, PSQI, and DES-II, scores at the final two-month follow-up assessment to the 12-month follow-up using difference scores in an independent t-test for a within-subject analysis with p value set at 0.05.

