9.0 Analyses

In general, nominal variables will be described in terms of frequencies and percentages and analyzed using chi square analysis. Ordinal and non-normal continuous variables will be described using sample median and range, and analyzed by non-parametric statistical tests, and approximately normal variables will be described using sample mean and standard deviations and analyzed by parametric statistical tests. All statistical tests will be two-sided and a difference resulting in a p-value of less than or equal to 0.05 will be considered statistically significant. All p-values will be rounded to and displayed in four decimals. If a p-value less than 0.0001 occurs it will be shown in tables as <0.0001. For any analysis that is called out as parametric, e.g. t-test, the parametric assumptions will be examined. If necessary, nonparametric analyses will be utilized, e.g. Wilcoxon rank-sum test.

Clinical data will be presented in tabular format. Data not subject to analysis according to this plan will not appear in any tables or graphs, but will be included in the data listings. Analyses will be carried out with SAS Version 9.3 or higher. Selected results may be presented graphically using standard graphical software.

Post-hoc exploratory analyses not identified in this SAP may be performed to further examine the study data. These analyses will be clearly identified as such in the final clinical study report.

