9.9.2.1 Secondary Efficacy Analyses at Secondary Endpoints

Assess 3 vs. 2 experimental MDMA sessions

For the CAPS, the absolute changes in the measure from the primary endpoint to end of Stage 1 for the 100 and 125 mg groups will be compared with t-tests. In the crossover subjects (40 mg) the absolute changes in the measures from the secondary (visit 27) endpoint to end of Stage 2 (visit 32) will be compared with t-tests.

Crossover Subject Analyses

CAPS data from subjects assigned to the 40 mg group in Stage 1, i.e. ‘crossover population,’ will be analyzed by t-tests on difference scores from primary endpoint (visit 12) in Stage 1 to secondary endpoint in Stage 2 (visit 27). Additionally, the following measures’ total scores will be analyzed in this same fashion: CAPS, PTGI, BDI-II, GAF, PSQI, DES-II, PDS.

Long-term Follow-up

For the CAPS, PDS, PTGI, BDI-II, GAF, PSQI, and DES-II, the absolute changes in the measures from baseline to the long-term follow-up visit (one year post final experimental year) will be compared with t-tests. The absolute changes in the measures from long-term follow-up to End of Stage 1 (visit 17, 100 mg and 125 mg) or long-term follow-up compared to End of Stage 2 (visit 32, 40 mg) will be compared with t-tests.

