9.9.3.1 Process Measures

States of Consciousness Questionnaire (SOCQ)

Descriptive statistics will be computed for SOCQ scores completed after each MDMA-assisted psychotherapy session, and SOCQ scores will be compared by initial dose using ANOVA for overall differences and t-tests for pairwise comparisons for each experimental session. The data will be explored for effects of dose on composite and total SOCQ scores.

Long-term Follow-up Questionnaire (LTFU Questionnaire)

The LTFU Questionnaire nominal variables will be described in terms of frequencies and percentages, while ordinal and non-normal continuous variables will be described using sample mean, standard deviations, and range.

Belief of Condition Assignment

In order to compare the therapists', independent raters', and subjects' belief of treatment group to actual MDMA dose received in each blinded session, the number and frequency of correct guesses will be calculated and depicted by dose group and study role (subject and each therapist).

Subject's Perceptions of Experimental Sessions

Descriptive statistics will be calculated for subject's perceptions of experimental sessions. Mean, standard deviation and range of individual responses and sum of items #1-4 will be examined. For the 100 and 125 mg group, within-subjects t-tests will be performed on subject's perceptions at Stage 1 primary (visit 12) and end of stage 1 (visit 17) endpoints. The same analysis will be performed for 40 mg group, but data will be from Stage 2 secondary (visit 27) and end of stage 2 (visit 32) endpoints.

Reactions to Research Participation Questionnaire (RRPQ)

Frequency of response will be tabulated for 'reasons for participation' across Stage 1 treatment groups. Descriptive statistics will be computed for total scores for subscales and displayed by Stage 1 conditions.

Adherence to the Treatment Manual

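### The 12-month durability comparison names an independent t-test for a within-subject question, and the SAP does not clearly correct it

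*Protocol*

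**What the plan says.** Protocol section 12.0 compares CAPS, PDS, PTGI, GAF, BDI-II, PSQI and DES-II "scores at the final two-month follow-up assessment to the 12-month follow-up", and the method given is "using difference scores in an independent t-test for a within-subject analysis with p value set at 0.05". Both scores come from the same person; Protocol section 5.2.10 schedules the 12-month visit for all subjects.

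SAP section 9.9.2.1 has two long-term comparisons. One uses "the absolute changes in the measures from baseline to the long-term follow-up visit". The other matches the protocol's. For subjects who began on an active dose it takes "The absolute changes in the measures from long-term follow-up to End of Stage 1 (visit 17, 100 mg and 125 mg"). For subjects who began on the comparator dose, the wording is "or long-term follow-up compared to End of Stage 2 (visit 32, 40 mg) will be compared with t-tests". Neither is described as paired, one-sample or between-group.

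Both documents name a paired test elsewhere. For the tinnitus and pain scale, Protocol section 12.0 uses an independent t-test between conditions; if only one condition has data, "then a paired t-test will be performed comparing baseline and primary endpoint" scores. SAP section 9.9.3.1 states that "within-subjects t-tests will be performed on subject's perceptions at Stage 1 primary (visit 12) and end of stage 1 (visit 17) endpoints". The general rule in SAP section 9.0 is "All statistical tests will be two-sided and a difference resulting in a p-value of less than or equal to 0.05" counts as significant.

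**The concern.** The question at 12 months is whether the improvement seen at the final two-month visit is kept. That concerns each subject's change, so the natural test is a one-sample t-test on the differences, which is the paired t-test. The protocol asks for a within-subject analysis but names a test for two unrelated groups.

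The word independent cannot simply be taken as a slip for paired. The tinnitus and pain rule in the same protocol section uses the two terms as alternatives. That section also applies independent-sample t-tests to difference scores when it compares the combined active groups with the comparator, for CAPS and again for RBANS and PASAT. The mention of difference scores therefore does not by itself turn the sentence into a paired test.

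Long-term effect is a stated secondary objective in both documents. With 23 to 26 subjects, the choice between a paired and an unpaired test can decide whether a moderate mean worsening is seen, and the plan leaves that choice open.

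**Working it through.** **Inputs from the documents.** N is 23 (Protocol section 5.3) or 26 (SAP section 6.0). Tests are two-sided at 0.05. The documents give no SD, no two-month to 12-month correlation and no power for this comparison.

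**Assumptions.** Equal SD at both visits, bivariate normal scores, a mean worsening of 0.4 SD, and r from 0 to 0.7. The nearest correlation in the documents is the PDS retest figure of 0.74 (Protocol section 5.1.1), but it covers two weeks to one month, not the longer gap between these visits.

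**Check of method on the plan's own figure.** Protocol section 12.1 gives power 0.33 for 18 versus 5 at an effect size of 0.8 (primary endpoint). The noncentral t calculation, two-sided at 0.05, gives 0.327, so it reproduces. At 1.1 it gives 0.546, matching the printed 0.55, which the text labels an effect size but which is a power.

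**Three readings of the 12-month sentence.**

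(a) *One-sample t-test on each subject's difference.* This is the paired test. Its SE is s√(2(1−r)/n) and its type I error is 0.05. Nothing is lost, but the word independent has to be ignored.

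(b) *Independent t-test on change scores between dose groups.* The SE is valid. The tested quantity is the mean change in one group minus the mean change in another. If every group worsens by the same amount δ, it equals δ − δ = 0, and the test rejects about 5% of the time however large δ is. A simulated uniform 10-point worsening, 125 mg versus 100 mg at 12 v 9 and at 9 v 9, gave rejection of 0.05. Durability is not tested.

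(c) *Independent t-test on the two visits' raw scores.* The SE used is s√(2/n). The ratio to the correct one is √(2/n) / √(2(1−r)/n) = 1/√(1−r). For n = 26 and r = 0.5, in SD units: √(2/26) = 0.277 against √(1/26) = 0.196, a ratio of 1.41.

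Power for the paired test uses a standardised change of 0.4/√(2(1−r)). For r = 0.5 that is 0.4; multiplied by √26 it gives a noncentrality of 2.04 on 25 degrees of freedom and power 0.50. Power and type I error for the raw-score test come from simulation with 200,000 replicates.

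| r | SE ratio under (c) | Type I error under (c), n = 26 | Power, n = 26: independent vs paired | Power, n = 23: independent vs paired |
|---|---|---|---|---|
| 0 | 1.00 | 0.050 | 0.29 vs 0.28 | 0.26 vs 0.25 |
| 0.3 | 1.20 | 0.021 | 0.26 vs 0.38 | 0.23 vs 0.34 |
| 0.5 | 1.41 | 0.007 | 0.23 vs 0.50 | 0.19 vs 0.45 |
| 0.7 | 1.83 | 0.0008 | 0.18 vs 0.72 | 0.15 vs 0.66 |

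For a larger worsening of 0.8 SD at n = 26 the gap is small: 0.89 against 0.97 at r = 0.5, and 0.93 against 0.999 at r = 0.7.

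**The case against.** The strongest reply is that the sentence itself specifies difference scores and a within-subject analysis. A test on raw scores from two supposedly unrelated groups uses neither. A sensible analyst would run the one-sample test on differences, and no error would follow. The SAP, which reflects Amendment 6, drops the word independent and works with changes, so the pairing is kept. Its clause for the 40 mg subjects concerns a single group, where a between-group test is impossible. The crossover paragraph in the same SAP section uses t-tests on difference scores for one group, so there the wording already means a within-subject test.

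Much of this stands, and it limits the point. It does not remove it. The protocol still names a test that does not fit its stated purpose. The SAP clause for the 100 mg and 125 mg subjects can still be read as a comparison of the two arms. The nonparametric example in SAP section 9.0 is the rank-sum test, which is itself unpaired.

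A reader might go further and infer that the 12-month standard errors are wrong, or that relapse will be hard to detect. The documents do not support either. The inflated standard error and lost power arise only under reading (c), and their size depends on a correlation that is not given; at r = 0 they vanish. Neither document specifies a confidence interval for this comparison. No t-test on means, paired or not, identifies individual relapse. Nor does either document say that a non-significant result will be taken as proof of durability: Protocol section 12.0 also plans 12-month effect sizes, and SAP section 9.9 plans descriptive statistics by group.

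**Conclusion.** The point holds as a contradiction in the protocol that the SAP does not clearly resolve. Both readings that honour the word independent fail the durability question: (b) asks a different one, and (c) discards the pairing. Reading (a) is correct, but the reader has to supply it.

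The size is conditional. Under (c), for an assumed mean worsening of 0.4 SD, the loss of power at n = 26 runs from none at r = 0 to 0.54 (0.72 − 0.18) at r = 0.7; at n = 23 the pattern is the same. The error is conservative when r is positive, so the risk is a missed mean worsening and not a false alarm. Under (a) there is no loss. How many subjects will attend the 12-month visit is not known.

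This is a secondary analysis in a pilot that describes itself as underpowered, and the primary analysis is unaffected. The wording should be corrected because the remedy is specific and cheap. Confidence is high on the contradiction and low on any particular power figure.

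**What to change.** In Protocol section 12.0 and in the long-term follow-up paragraph of SAP section 9.9.2.1, replace the current wording with a sentence to this effect: *Within-subject change from the final two-month visit (V17 or V32) to long-term follow-up is tested with a paired (one-sample on differences) t-test and reported with a 95% confidence interval; the Wilcoxon signed-rank test is used if assumptions are not met.*

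If a comparison of these changes between dose groups is also wanted, state it as a separate analysis with its own test.

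The cost is one sentence in each document. No new data, visits or burden on subjects are involved.

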3.3 Safety Objectives

The safety objectives of the study are to monitor and assure safety of subjects during and after the experimental sessions by assessing physiological effects, psychological distress, adverse events, spontaneously reported reactions and suicidality.

- Suicidality will be assessed with the Columbia Suicide Severity Rating Scale (C-SSRS) during some visits prior to experimental sessions, twice during experimental sessions, and several times after each experimental session, with comparisons made between subjects in each condition.
- Assess cognitive function with the Paced Auditory Serial Addition Test (PASAT) and the Repeatable Battery for the Assessment of Neuropsychological Status (RBANS) at baseline and the primary endpoint by condition, and end of Stage 1/end of Stage 2 for maximal exposure.
- Subjective Units of Distress (SUD) and vital signs including blood pressure, heart rate, and temperature will be measured during each experimental session, and vital signs will be compared between subjects in each condition.
- Collect changes to pre-existing tinnitus and/or chronic pain symptoms using a visual analog scale, specifically in subjects with a medical history of tinnitus and/or chronic pain.
- Serious adverse events, adverse events, and spontaneously reported reactions will be collected during the study, as described in Section 8.5.

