5.3 Randomization and Subject Numbering

Prior to enrollment, subjects will be tracked with their initials and a screening number assigned sequentially starting at “S001”. Subjects who meet all inclusion and no exclusion criteria will be enrolled into the study and will be assigned a five-digit subject number. The first two digits will be “12” and will identify the protocol number. The next three digits identify the subject within the site and will be assigned sequentially, with 001 corresponding to the first subject enrolled, e.g. the first enrolled subject will be 12001, second 12002, etc.

In total, 23 subjects will be enrolled into the study. The randomized portion of the study will be blinded and there will be a 9:9:5 ratio between subjects in the active dose 1, active dose 2, and comparator dose conditions. An unblinded randomization monitor will generate the randomization list. Subjects will be assigned subject numbers, and subjects will be randomized in a blinded fashion. Upon enrolling a subject, the investigator will be provided with an Enrollment Code for that subject. Randomization numbers will be pre-printed on the container labels corresponding to doses for individual sessions. Randomization will be performed at least 24 hours before the experimental session for each subject. The therapists will utilize a web-based randomization program to obtain the container assignment for each experimental session. Blinded personnel will conduct all study evaluations in the randomized portion of the study until the blind is broken for each subject at the primary endpoint per protocol via the web-based randomization program. Detailed instructions will be provided to the site in a separate document.

If there is an emergency requiring knowledge of subject’s condition assignment, the blind may be broken for an individual subject. The investigator may be provided with the condition assignment in case of emergency through the web-based randomization system.

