The sponsor will compare baseline and primary endpoint RBANS and PASAT scores in each active dose group and comparator dose groups. Active dose 1 and active dose 2 RBANS and PASAT data will be tested for equivalence using confidence intervals. If the two groups are found to be equivalent, then outcomes for the active dose groups will be combined and will be tested for significant differences from the comparator group using difference scores in independent sample t-tests, with p value set at 0.05. If scores for active dose 1 are not equivalent to active dose 2, then analysis of variance (ANOVA) will be used to compare outcomes from all three groups. The sponsor will examine the effects of maximal exposure to MDMA on neurocognitive function using the RBANS and PASAT by performing a within-subject repeated measures ANOVA with time of administration as a within-subjects factor.

The sponsor will collect ratings of adherence to the treatment manual from specifically selected types of sessions. Descriptive statistics will be computed for each adherence scale within a given session. The sponsor will explore the factors and structure of the measures of adherence to assist in further development of adherence and competence measures. If sufficient data is available, the sponsor will correlate the mean adherence ratings for adherence scale and session type with Global CAPS scores to investigate the effects of adherence to the treatment manual on reduction in PTSD symptoms. If it is found that there are specific factors within the adherence scales, then the factor will be correlated with Global CAPS score.

Subjects who discontinue treatment prior to the primary endpoint will be asked to complete an outcome assessment prior to continuing to the long-term follow-up. The data from these subjects will be tested for equivalence to data from subjects completing the study per protocol. If found to be equivalent, data from these subjects will be presented as an exploratory Intent-to-treat analysis to examine results without bias towards subjects more likely to complete the study per protocol, with last observation carried forward.

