Formal analysis of Changes in Tinnitus and/or Pain visual analog scale scores will only occur if three or more subjects complete Changes in Tinnitus and/or Pain visual analog scale at baseline and primary endpoint. Likewise, formal between-groups analyses will not be performed if all primary endpoint scores are from subjects assigned to the same treatment group. Descriptive statistics will be presented on the difference between baseline and primary endpoint changes in Tinnitus and/or Pain visual analog scale scores in the full dose and comparator dose treatment groups.

Vital signs

Vital signs (heart rate, body temperature, systolic and diastolic blood pressure) will be summarized using descriptive statistics at baseline and at each post-baseline time point. Occurrences of systolic and diastolic blood pressure, heart rate, and body temperature readings above the pre-determined cutoff will be displayed with numbers and percentages by timepoint.

Paced Auditory Serial Addition Test (PASAT) and Repeatable Battery for the Assessment of Neuropsychological Status (RBANS)

RBANS and PASAT scores at baseline and primary endpoint will be compared in each active dose group and comparator dose groups using descriptive statistics. In an exploratory analysis, the effects of maximal exposure to MDMA on neurocognitive function using the RBANS and PASAT will be examined.

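### Neither the protocol's difference tests nor the SAP's arm-level descriptives for RBANS and PASAT show how much dose-related cognitive decline the data exclude

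*Protocol*

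**What the plan says.** Protocol section 3.3 lists cognition among the safety objectives: "Assess cognitive function with the Paced Auditory Serial Addition Test (PASAT) and the Repeatable Battery", at baseline and primary endpoint by condition, with a later assessment for maximal exposure. SAP section 4.3 repeats the objective.

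Protocol section 12.0 sets out the dose-group analysis in two branches. First, "Active dose 1 and active dose 2 RBANS and PASAT data will be tested for equivalence using confidence intervals"; no margin or confidence level is given. If the doses are judged equivalent, the pooled active group is "tested for significant differences from the comparator group using difference scores in independent sample t-tests, with p value set at 0.05". If they are not, "then analysis of variance (ANOVA) will be used to compare outcomes from all three groups". Maximal exposure is handled separately by "performing a within-subject repeated measures ANOVA with time of administration as a within-subjects factor", which is a time effect and not a contrast between doses.

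SAP section 9.9.4 plans neither dose-group test. RBANS and PASAT at baseline and primary endpoint "will be compared in each active dose group and comparator dose groups using descriptive statistics". Maximal exposure becomes an exploratory analysis with no stated method.

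On numbers, Protocol section 5.3 says "there will be a 9:9:5 ratio between subjects in the active dose 1, active dose 2, and comparator dose conditions". SAP section 6.0 gives 12:9:5 after Amendment 6. Protocol section 12.1 calculates power for CAPS only, says the study lacks power for small and moderate effects, and gives no power for secondary or exploratory measures.

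**The concern.** A safety objective asks how much harm the data are compatible with. A test at 0.05 does not answer that, because a non-significant result is what one expects with five comparator subjects even when there is a real loss. Separate descriptive tables for each arm do not answer it either: they give no between-arm difference and no measure of its uncertainty.

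Visit 12 cannot be made good later. After baseline and visit 12, RBANS and PASAT are scheduled only at visit 17, which is for active-dose subjects, and at visit 32, after comparator subjects have had open-label active doses. They are not scheduled at long-term follow-up. Protocol section 2.1 says the study is meant to yield effect-size estimates for safety as well as efficacy. For cognition by dose, neither document plans an estimate of the difference with an interval. The effect-size formula in SAP section 9.9 sits under the efficacy analyses, is for measures of interest, and comes with no interval.

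**Working it through.** **Inputs.** Pooled comparison 18 v 5 (Protocol 9:9:5) or 21 v 5 (SAP 12:9:5). Alpha is 0.05. Sidedness comes from SAP section 9.0: "All statistical tests will be two-sided". Normal data and equal SDs are assumed. The loss δ is in units of the SD of the baseline-to-visit-12 change score, the variable that the protocol's t-test uses. The value 0.5 is chosen for illustration; the documents set no margin.

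**Step 1: reproduce the protocol's own figure.** Two-sample t-test, noncentral t, df = n1 + n2 − 2, noncentrality = δ × √(n1·n2/(n1+n2)). For 18 v 5, √(90/23) = 1.978 and df = 21.
- δ = 0.8: noncentrality 1.583, power 0.327 (stated 0.33).
- δ = 1.1: noncentrality 2.176, power 0.546 (the protocol prints 0.55, worded as an effect size).

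Both match only as two-sided tests, so the same method is used below.

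**Step 2: pooled t-test for cognition.**
- 18 v 5, δ = 0.5: noncentrality 0.989, power 0.157, miss rate 84.3%.
- 21 v 5, δ = 0.5: √(105/26) = 2.010, noncentrality 1.005, power 0.162, miss rate 83.8%.
- δ = 0.8: missed 67% (18 v 5) or 66% (21 v 5) of the time.
- Loss detectable with 80% power: 1.49 SD (18 v 5) or 1.45 SD (21 v 5).

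**Step 3: ANOVA branch, both active arms 0.5 SD worse.** Noncentral F with 2 and N − 3 df, noncentrality = 0.5² × n_active × 5/N.
- 9:9:5: 0.25 × 90/23 = 0.978, power 0.119, miss rate 88%.
- 12:9:5: 0.25 × 105/26 = 1.010, power 0.123, miss rate 88%.

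**Step 4: the same loss in raw-score SD units.** With equal variances, SD of change = raw SD × √(2(1 − r)), where r is the pre-post correlation. A loss of 0.5 raw SD then equals 0.5/√(2(1 − r)) change-score SD. For 18 v 5:

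| r | loss in change-score SD | miss rate |
|---|---|---|
| 0.50 | 0.50 | 84% |
| 0.70 | 0.65 | 77% |
| 0.80 | 0.79 | 68% |
| 0.90 | 1.12 | 44% |
| 0.95 | 1.58 | 15% |
| 0.97 | 2.04 | 3% |

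Protocol section 5.1.2 quotes PASAT test-retest reliability of 0.90 to 0.97. If the trial's pre-post correlation were similar, the last three rows would be the relevant ones for PASAT. For RBANS the protocol calls test-retest reliability good but gives no figure, so its row is unknown.

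**Step 5: what an interval would show.** Expected two-sided 95% half-width = t(0.975, df) × √(1/n1 + 1/n2), in change-score SD:
- 18 v 5: 2.080 × 0.506 = 1.05
- 21 v 5: 2.064 × 0.498 = 1.03
- 9 v 5: 2.179 × 0.558 = 1.22
- 12 v 5: 2.131 × 0.532 = 1.13

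In raw-score SD units for 18 v 5, this is 1.05 × √0.2 = 0.47 at r = 0.90 and 1.05 × √0.06 = 0.26 at r = 0.97. How informative the contrast is therefore depends on a correlation that is not known in advance. An interval shows this after the fact; a p-value or arm means do not.

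**The case against.** The strongest reply is that this is a declared pilot. Protocol section 12.1 admits low power, SAP section 7.0 repeats the caveat, and the SAP has already dropped the test, so no significance verdict at visit 12 can miss anything. Part of this stands: if the SAP governs, the 84% and 88% describe analyses that will not be run. But the SAP removes the p-value without supplying a difference or an interval, and low power is itself a reason to report one.

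A reader might infer more than the documents support:

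- **That the pooled t-test is the only dose-group test.** It is not; the protocol also names the three-group ANOVA. That branch uses the same five comparators and has lower power in the case examined.
- **That a loss of half an SD in test scores would be missed 84% of the time on both instruments.** The figure is in change-score units. At the PASAT reliability the protocol quotes, the raw-unit miss rate would be about 44% to 3%.
- **That the trial cannot exclude losses below about 0.85 SD.** The one-sided 95% bound of 0.87 (18 v 5) or 0.85 (21 v 5) applies only if the observed difference is exactly zero, only to the pooled contrast, and only in change-score units.
- **That the contrast bounds the cognitive harm of MDMA.** The comparator is 40 mg MDMA, so a loss common to all arms would not appear in it.
- **That the sponsor will report a null result as proof of no harm.** No passage says so. Section 12.1 specifies its meta-analyses as being of CAPS scores, and section 2.1 speaks of combining the data without naming cognition.

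**Conclusion.** The point holds as a gap in estimation and reporting. Both protocol tests look for a difference against five subjects and miss a loss of 0.5 change-score SD about 84% (pooled t-test) and 88% (ANOVA) of the time, with almost the same figures under either allocation. The SAP's replacement gives arm-level summaries only. Neither document yields an active-minus-comparator difference with an interval, so neither shows how much added decline at 100 mg or 125 mg the data exclude.

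The figures assume normal data, equal SDs, two-sided 0.05, complete data at the planned numbers and the same loss in both active arms. The raw-unit figures also assume equal variances before and after treatment. The point does not depend on 0.5 SD being the right threshold, and it does not call for more subjects. It should be acted on because the remedy is cheap and visit 12 is the only randomised cognitive comparison.

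**What to change.** In SAP section 9.9.4, and in Protocol section 12.0 in place of the 0.05 rule, report the active-minus-comparator difference in baseline-to-visit-12 change for RBANS total and PASAT. Give it for each active dose and for both together, with a 95% confidence interval in raw score units and in change-score SD units. List each subject's change by dose.

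Add three statements:

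1. A non-significant or similar-looking result will not be reported as absence of a cognitive effect.
2. The comparator is 40 mg MDMA, so the contrast bounds only the added effect of the higher doses.
3. The expected two-sided 95% half-width is about 1.03 to 1.05 change-score SD for the pooled contrast, and about 1.13 to 1.22 for a single active arm of 12 or 9 against 5.

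Do not write a fixed excluded loss into the plan; read the bound from the observed interval.

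The cost is SAP and protocol wording plus one table and a listing on data already collected. The cognitive safety statement will read less favourably.
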